Official Title	Pharmacy Delivery to Expand the Reach of PrEP in Kenya: Cluster-randomized Control Trial
NCT Number	NCT05842122
Document Type	Statistical Analysis Plan
Document Date	12/16/2025

Pharmacy delivery to expand the reach of PrEP in Kenya: cluster-randomized control trial

Pharm PrEP cRCT

Statistical Analysis Plan

Version 1.9

16 December 2025

NCT05842122

Based on protocol version 2.2 dated 23 July 2025

FINAL

[name]

Contents

Introduction	4
1. Study Objectives and Overview	4
2. Study Population	5
3. Study Outcomes	6
4 Study Design	9
4.2 Trial	9
4.3 Intervention	10
4.4 Randomization	10
4.5 Sample size and power	11
5 Planned Analyses	14
6 General Statistical Considerations	14
6.2 Data sources	14
6.3 Descriptive statistics	17
6.4 Statistical testing and models	17
6.5 Exposure groups	17
6.6 Analysis populations	17
6.7 Missing values	18
7 Data Analysis	18
7.2 Study enrollment	18
7.3 Pharmacy characteristics	18
7.4 Characteristics at enrollment	18
7.5 Outcomes	18
7.6 Safety	22
7.6.1 HIV seroconversion	22
7.7 Post-unblinding update: December 16, 2025	23

Introduction

This statistical analysis plan (SAP) describes the statistical procedures and analyses and data displays that address study objectives specified in protocol version 1.1 of the Pharm PrEP cRCT (a study of pharmacy-delivered PrEP/PEP in Kenya).

New versions of the SAP will be issued to document updates and changes in the plan. Any meaningful changes or additions to this SAP (e.g., in response to protocol amendments or violations of assumptions underlying pre-planned analyses), and the timing of such changes in relation to timing of performing the analysis will be documented in the SAP.

1. Study Objectives and Overview

Protocol title	Pharmacy delivery to expand the reach of PrEP in Kenya: cluster-randomized control trial
Short title	Pharm PrEP cRCT
Design	Cluster-randomized controlled trial
Study exposures	Each pharmacy is randomized to either provision of PrEP/PEP in pharmacies either provided by a pharmacist for free (Arm 1), for a fee (Arm 2), or by an HTS counselor for free (Arm 3); or referral to a clinic for PrEP/PEP (Arm 4, standard of care)
Population	Pharmacies must be registered; pharmacists must be licensed and HTS counselors must be certified; enrolled clients must be adults (≥ 16 years old), at risk of HIV, and eligible for PrEP/PEP (according to the prescribing checklist)

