- PrEP continuation: the number of participants at each pharmacy that initiated PrEP at the pharmacy or clinic and returned to the pharmacy or clinic and refilled PrEP **within 60 days** of initial pharmacy-based screening. *Comparisons between intervention arms and the control will rely on self-report from the 60-day client survey, while comparisons between intervention arms will employ pharmacy records.*

Secondary outcomes include those related to PrEP initiation, PrEP continuation, PrEP adherence, PEP initiation, PEP-to-PrEP transition, and repeat PEP use.

- PrEP initiation: the number of participants at each pharmacy that initiated (i.e., were dispensed) PrEP at the pharmacy or clinic **within 270 days** of initial pharmacy-based screening
- PrEP continuation:
 - The number of participants at each pharmacy that initiated PrEP at the pharmacy or clinic and returned to the pharmacy or clinic and refilled PrEP **within 270 days** of initial pharmacy-based screening (regardless of any gaps in pill coverage).
 - The number of participants at each pharmacy that initiated PrEP at the pharmacy or clinic and **refilled PrEP at least twice within 270 days** of initial pharmacy-based screening (regardless of any gaps in pill coverage).
 - The number of participants at each pharmacy that initiated PrEP at the pharmacy or clinic and refilled PrEP more than 7 days after their expected refill date (i.e., stopping and restarting, also referred to as “PrEP reinitiation”) **within 270 days** of initial pharmacy-based screening.
- PrEP adherence: The median adherence score (0-100) among participants at each pharmacy who initiated PrEP at the pharmacy or clinic –using the Wilson et al. scale (2020, *AIDS*)—as measured at **60 days** following initial pharmacy screening.
- PEP initiation: the number of participants at each pharmacy that initiated (i.e., were dispensed) PEP ≥ 1 times at the pharmacy or clinic within 3 days, as measured at **60 days** and **270 days** following initial pharmacy screening.
- PEP-to-PrEP transition: the number of participants at each pharmacy that successfully completed PEP (tested negative or self-reported testing negative for HIV between 28 and 45 days after initiating PEP at the pharmacy) **and** initiated PrEP at the pharmacy or clinic as measured at **60 days** and **270 days** following initial pharmacy screening.

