In particular, to estimate power, it was assumed that the average pharmacy flow was the same across the four arms; there is no a priori reason to assume otherwise. We further assumed a coefficient of variation (CV) of 0.25. The coefficient of variation characterizes the variability in number of PrEP initiations (relative to pharmacy size) across pharmacies. While this is difficult to know ahead of time, it is typically <0.25 (Hayes and Bennett, *IJE*, 1999). A CV of 0.25 would roughly correspond to a situation where, for example, the average number of PrEP initiations was 20/pharmacy, and 95% of pharmacies had between 10 and 30 initiations (assuming equal flow across pharmacies); this seems to be a reasonable degree of variability in our setting. Given that the analyses will include comparisons of Arms 1, 2, and 3 vs. 4, we used a Bonferroni correction to our alpha level (two-sided alpha = 0.05/3) for the PrEP 60-day initiation/continuation outcomes and the combined PrEP/PEP outcomes (primary and key secondary outcomes).

Based on the hypothesized number of PrEP/PEP initiations and continuations in **Table 3**, we estimated the power would be very high for comparing Arms 2 and 3 to Arm 4 for PrEP initiation

and continuation (primary outcomes) and the combined PrEP/PEP initiation and continuation outcomes (key secondary outcomes; **Table 4**). For the Arm 1 vs. Arm 4 comparisons, the power is estimated to be 80% for PrEP initiation (as designed), 100% for the combined PrEP/PEP initiation outcome, and lower for the continuation outcomes.

→ **Primary outcome assessment will be completed after a total of 1,119 PrEP initiations are achieved. A study duration of 20 months of implementation is targeted.**

Table 3: Number of PrEP, PEP, and PrEP/PEP initiations and continuations per pharmacy (k=15/arm, k=60 total) for >80% power in our PrEP outcomes of interest

	1: Client-sustained	2: Implementor-sustained	3: HTS supported	4: Referral (SOC)	TOTAL (across 60 pharms)
PrEP initiations	16.13	22.18	26.21	10.08	1,119
PEP initiations	32	48	64	16	2,400
Total PrEP/PEP initiations	48.13	70.18	90.21	26.08	3,519
PrEP continuations	8.06 (50% of initiations)	15.52 (70% of initiations)	20.97 (80% of initiations)	6.05 (60% of initiations)	759
PEP continuations	4.34 (13.6% of initiations)	9.12 (19.0% of initiations)	13.90 (21.7% of initiations)	2.61 (16.3% of initiations)	450

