6.2 Data sources

The following data sources will be used to address the objectives (detailed in **Table 5**):

- Pharmacy records: intervention arms only, Arms 1-3 (i.e., not SOC arm, Arm 4)
 - Items on Prescribing Checklist, including PEP/PrEP dispensing data, age, sex, marital/relationship status, behaviors associated with HIV risk, HIV test result
 - Other services/products purchased
- Clinic records: SOC arm only
 - Items on the Clinical Encounter Form akin to those in the study's Prescribing Checklist
- Brief client surveys: all arms
 - Brief demographics
 - Whether the participant initiated PrEP and/or PEP and, if so, where
 - Whether the participant has refilled PrEP and, if so, where
 - Whether the participant is still taking PrEP/PEP as of today
 - If the participant is still taking PrEP/PEP, how many PrEP/PEP pills they swallowed in the past 7 days
 - PrEP adherence
 - Select HIV risk behavior questions

- Extended client survey: all arms
 - Extended demographics
 - Alcohol use
 - Sexual and mental health
 - HIV risk behaviors
 - Fertility
 - Social harm
 - Acceptability of pharmacy model in which they received PrEP/PEP services
 - Quality of care perceptions Fidelity of services received
 - Willingness to pay
- Provider surveys: all arms
 - Provider demographics
 - Acceptability of pharmacy-delivered PrEP/PEP
 - Feasibility of pharmacy-delivered PrEP/PEP
 - Self-efficacy to delivery PrEP/PEP services at pharmacies
 - Organizational Readiness for Change (ORIC)
 - Willingness to charge
- Client in-depth interviews: all arms
 - Model acceptability
 - Model appropriateness
 - Acceptability of modifications
 - Appropriateness of modifications
- Provider in-depth interviews: all arms
 - Acceptability
 - Feasibility
- Technical assistance (TA) reports
 - Adaptations

Data from the Maisha Meds application on PrEP/PEP delivery/dispensing, survey data, audio files from interviews, and interview transcripts will be stored on secure electronic platforms that meet all data security requirements (e.g., REDCap, Dedoose). Table 5 below summarizes the outcomes and data sources.

Table 5. Data sources

PRIMARY/ SECONDARY	OUTCOME	TIMING	DATA SOURCE
Primary	PrEP initiation	By 60 days	Brief client survey Pharmacy records* Clinic records*
	PrEP continuation	By 60 days	
Secondary	PrEP initiation	By 270 days	
	Any PrEP continuation	By 270 days	
	At least 2 PrEP refills	By 270 days	
	Any stopping and restarting PrEP (i.e., PrEP reinitiation)	By 60 and 270 days	

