We will estimate the ratio of PrEP initiation rates (number of initiations per clients served at the pharmacy, accounting for pharmacy volume over the implementation period) comparing each intervention arm to the SOC arm using a Poisson generalized linear model with log link and robust standard errors. The model will allow for overdispersion to account for increased variability in rates. The outcome will be number of self-reported PrEP initiations from the 60-day brief client survey in each pharmacy. A cluster-level analysis was chosen for the outcome of PrEP initiation because the number of individuals enrolling in the study at a given pharmacy was found to be heavily dependent upon the study arm of the pharmacy. Thus, the available denominator for the individual-level PrEP initiation outcome, number of individuals enrolled in the study, was a poor proxy for the quantity of interest, number of pharmacy PrEP candidates (i.e., individuals determined at risk of HIV acquisition who meet the pharmacy PrEP prescribing checklist criteria). Instead, we will pursue a cluster-level analysis where the outcome is number of initiations at each pharmacy and we account for pharmacy volume as a way to make fair comparisons across pharmacies.

The model will include study arm as a four-level categorical (nominal) variable and a continuous offset variable reflecting pharmacy volume (number of clients per unit time). Pharmacy volume will be measured as the number of transactions per month. Estimates of monthly volume will be obtained up to three times in each pharmacy during the course of the study (to account for seasonal variations); missing observations will be imputed, and we will take the average of the three assessments. To account for the stratified randomization procedure, we will adjust for county as a categorical (nominal) variable. As noted in Section 6.7, our missing imputation strategy (i.e., imputing missing outcome data as failures) will not affect the primary analysis of the pharmacy-level count data and will only influence the secondary analysis described in Section 7.5.1.3.

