7.5.2 Secondary and tertiary outcomes

The analysis of the secondary outcomes of PrEP initiation within 270 days, any PrEP continuation within 270 days, at least 2 PrEP refills, any stopping and restarting PrEP, PEP initiation, PEP-to-PrEP transition, recurrent PEP use, PrEP/PEP initiation, PrEP/PEP continuation, PrEP adherence and the tertiary outcome of follow-up HIV testing will be similar to those described in Sections 7.5.1.1. Furthermore, the secondary analyses proposed in Section 7.5.1.3 will be performed for these outcomes (as appropriate for the outcome), with the exception of the secondary analysis investigating interactions. For the analysis of PrEP initiation with 270 days, the sensitivity analysis described in Section 6.7, in which PrEP initiation at 60 days is used to impute missing PrEP initiation at 270 days, will be performed.

For the exploratory outcome of PrEP coverage, descriptive statistics in each arm will be provided.

The tertiary outcomes (including acceptability, appropriateness, willingness to pay/charge, feasibility, and adaptations) will be summarized using descriptive statistics when assessed quantitatively and analyzed using a combination of inductive and deductive approaches (e.g., thematic content analysis) when assessed qualitatively. Similarly, the HIV risk behavior outcomes will be analyzed descriptively. No formal statistical comparisons will be performed for these tertiary outcomes.

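### The PEP-to-PrEP transition definition counts only PEP started at the pharmacy, so read literally the referral arm scores essentially nothing and rate ratios against it cannot be estimated

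*SAP*

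**What the plan says.** **The definition.** SAP Section 3 requires two things for a PEP-to-PrEP transition. The first is successful PEP completion, meaning the client "tested negative or self-reported testing negative for HIV between 28 and 45 days after initiating PEP at the pharmacy". The second is PrEP initiation, which may take place at the pharmacy or a clinic. The PEP initiation outcome, listed just before it, counts PEP dispensed "at the pharmacy or clinic within 3 days, as measured at" 60 and 270 days.

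**The control arm.** Section 1 describes the fourth arm as "or referral to a clinic for PrEP/PEP (Arm 4, standard of care". Section 6.2 limits one data source as follows: "Pharmacy records: intervention arms only, Arms 1-3 (i.e., not SOC arm, Arm 4".

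**The analysis.** Section 7.5.2 lists "PEP initiation, PEP-to-PrEP transition, recurrent PEP use" among the outcomes whose analyses "will be similar to those described in Sections 7.5.1.1". Section 7.5.1.1 estimates rate ratios "comparing each intervention arm to the SOC arm using a Poisson generalized linear model with log link and robust standard errors".

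**The planning figures.** Section 4.5 uses PEP continuation to mean a PEP user who goes on to PrEP. For Arm 4, Table 3 gives "2.61 (16.3% of initiations") per pharmacy.

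**The concern.** The pharmacy-only condition sits on the PEP step and nowhere else in the definition. In the arms that deliver PEP on site it excludes few clients or none. In the referral arm it excludes the ordinary route to PEP. An arm that cannot score is then the reference level of a log-link model. The model either gives no finite ratio or, if a few stray events are recorded, gives a very large one that reflects the definition and not the intervention.

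Timing adds to the problem. Section 7.7 records that the team was unblinded on November 6, 2025. If the programmer resolves the wording silently in code, that is an undocumented choice of outcome definition made after unblinding.

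**Working it through.** **1. Reproduce the planning figures.** Table 3 gives PEP continuations per pharmacy of 4.34, 9.12, 13.90 and 2.61 in Arms 1 to 4, with 15 pharmacies per arm.

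- Total: 15 x (4.34 + 9.12 + 13.90 + 2.61) = 15 x 29.97 = 449.6, against 450 stated.
- Arm 4 share: 2.61 / 16 PEP initiations = 16.3%, as stated.
- Arm 4 total: 15 x 2.61 = 39.2.

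**2. Check that the Arm 4 transitions enter the power figures.** Arm 4 combined continuations are 6.05 + 2.61 = 8.66. The unmatched cluster formula for rates is

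power = Φ( √[ (k−1)(λ1−λ0)² / (λ1 + λ0 + CV²(λ1² + λ0²)) ] − z(1−α/2) )

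with k = 15, CV = 0.25 and two-sided α = 0.05/3, so z = 2.394. For Arm 1 against Arm 4, λ1 = 12.40 and λ0 = 8.66:

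- numerator: 14 x 3.74² = 195.8
- denominator: 21.06 + 0.0625 x 228.76 = 35.36
- √(195.8 / 35.36) = 2.353
- power: Φ(2.353 − 2.394) = 48.4%, against 48% in Table 4.

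The same formula gives 80.1% for PrEP initiations (80% stated) and 23.2% for PrEP continuations (23% stated). The planning therefore relies on a non-zero Arm 4 transition count.

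**3. Compare the two readings of the outcome.**

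| | PEP started at pharmacy or clinic (as Table 3 implies) | PEP started at pharmacy only (as Section 3 reads) |
|---|---|---|
| Arm 4 transitions | at most about 39 | essentially 0 |
| Arm 1 / Arm 4 | 4.34 / 2.61 = 1.66 | 4.34 / 0, undefined |
| Arm 2 / Arm 4 | 9.12 / 2.61 = 3.49 | 9.12 / 0, undefined |
| Arm 3 / Arm 4 | 13.90 / 2.61 = 5.33 | 13.90 / 0, undefined |

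The figure of 39 is an upper one. Table 3 counts PEP users who move to PrEP, while Section 3 also requires a negative test in the 28-45 day window, which can only lower the count or leave it unchanged.

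If Arm 4 recorded a single stray event (an assumption), the Arm 1 ratio at equal pharmacy volume would be 15 x 4.34 / 1, or about 65. It would be finite but meaningless.

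**4. Fit the planned model.** Counts were simulated with the Table 3 means, the Table 1 arm-by-county layout, between-pharmacy CV 0.25, equal pharmacy volume (an assumption) and robust standard errors.

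- Arm 4 mean 2.61: one draw gave stable ratios of 2.5, 5.2 and 7.3.
- Arm 4 at zero: the Arm 1 ratio was about 3 x 10⁴ at 10 iterations, 7 x 10⁸ at 20 and 1.5 x 10¹³ at 30, and the robust standard errors broke down. No finite estimate exists.

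**5. Does the revised imputation in Section 7.7 help?** No. It draws non-responders' outcomes with the success proportion seen among responders in the same pharmacy. Where that proportion is 0, the imputed count is 0.

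**6. Possible carry-over.** The combined PrEP/PEP continuation outcome counts clients who started PEP and moved to PrEP, with no pharmacy-only limit in its own text. If the code reused the transition rule, the planned Arm 1 to Arm 4 ratio would move from 12.40 / 8.66 = 1.43 to 12.40 / 6.05 = 2.05.

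**The case against.** The best defence is that this is a slip of wording and that the intention is plain. PEP initiation and combined initiation both admit clinic starts. The brief survey, given in all arms, asks whether PEP was started and where. The definition itself accepts a self-reported negative test. The SAP also uses the word pharmacy loosely: the Table 2 caption calls initiations in all four arms pharmacy-based. On this view a sensible programmer would count clinic starts in Arm 4. That is a fair account of what was meant, and it makes the repair easy. It does not remove the conflict, because no section corrects the wording and Section 7.7 does not touch it.

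Two further points stand. First, the SAP never says outright that Arm 4 pharmacies dispense no PEP. This is a strong inference from the arm description and the record sources, hence essentially zero and not zero by definition. Second, the outcome has no row in Table 4 and is not among the primary or key secondary outcomes.

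A reader might infer more: that transitions cannot be measured under referral, that 39 events are lost, or that the trial's main comparison is compromised. The documents do not support these readings. The survey asks where PEP was started, 39 is an upper figure, and the primary outcomes do not use this definition. Comparisons among Arms 1-3 come from pharmacy records and remain estimable. A permutation test against Arm 4 would still return a p-value, but it would be testing the definition.

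**Conclusion.** The point holds for the comparisons of Arms 1-3 with Arm 4 on one secondary outcome, at 60 and 270 days. As written, the outcome rule conflicts with the neighbouring PEP initiation definition and with Table 3. Applied literally, it replaces a planned Arm 4 count of at most about 39 with essentially none, and the three rate ratios cannot be estimated. This rests on Arm 4 pharmacies not dispensing PEP.

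Any effect on the combined PrEP/PEP continuation outcome is conditional on how its transition component is programmed. Nothing in the text carries the limit over.

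At the Table 3 counts, admitting clinic starts would give the Arm 1 comparison about 60% power at two-sided 0.05: Φ(√[14 x 1.73² / (6.95 + 0.0625 x 25.65)] − 1.96) = Φ(2.213 − 1.960). The Arm 2 and Arm 3 comparisons would exceed 99%. The negative-test condition may reduce the counts below those in Table 3.

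**What to change.** 1. In Section 3, end the PEP completion condition with *after initiating PEP at the pharmacy or clinic*. Enter it in Section 7.7 as a dated, disclosed post-unblinding clarification that cites Table 3 as evidence of the planned meaning.
2. State the data sources: the client survey for comparisons with Arm 4, and pharmacy records for comparisons among Arms 1-3, as Sections 7.5.1.3 and 7.5.2 already provide.
3. Confirm that the survey or clinic records can supply the 28-45 day negative test in Arm 4. The brief-survey items listed in Section 6.2 name no HIV test date, although Table 5 assigns follow-up HIV testing to the client surveys. If the window cannot be derived in Arm 4, say so and report that limitation with the comparison.
4. Confirm in the code that the combined PrEP/PEP continuation outcome does not inherit the pharmacy-only limit.

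The text change is two words, and the derivation checks are short. The real costs are the disclosure that a definition was clarified after unblinding and the check on the Arm 4 test data, which could show that the wording change alone is not enough.

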Study size	At least 1,119 PrEP initiations and 2,400 PEP initiations for the cluster-randomized control trial
Study follow-up	At least 20 months for accrual (until sample size achieved) plus follow-up of up to 270 days.
Study sites	60 private pharmacies in Kenya (Nairobi; Kiambu; Kisumu/Siaya; and Homa Bay/Migori).
Objective	Quantify the effect of three models of pharmacy-delivered PrEP/PEP (sustained by clients; sustained by implementors; and sustained by implementors with support from HTS counselors) compared to pharmacy referral to clinic-based PrEP/PEP services (SOC) on PrEP/PEP outcomes and implementation outcomes
Outcomes	Primary: 
• PrEP initiation within 60 days of enrollment;• PrEP continuation (i.e., one refill) by 60 days

Secondary:

- PrEP initiation within 270 days;
- Any PrEP continuation within 270 days;
- At least 2 PrEP refills within 270 days;
- Any stopping and restarting PrEP (i.e., PrEP reinitiation);
- PEP initiation within 60 and 270 days;
- PEP-to-PrEP transition by 60 and 270 days;
- PrEP-to-PEP transition by 60 and 270 days;
- Recurrent PEP use by 60 and 270 days;
- PrEP adherence at 60 days;
- PrEP/PEP initiation within 60 and 270 days;
- Any PrEP/PEP continuation by 60 and 270 days

Tertiary:

- Follow-up HIV testing by 60 and 270 days;
- Behaviors associated with HIV risk at 60 and 270 days;
- PrEP coverage (exploratory)
- Acceptability; quality of care perceptions; willingness to pay; fidelity (client outcomes); acceptability; feasibility; adaptations; perceived self-efficacy; willingness to charge (provider/counselor outcomes); sustainability (pharmacy outcome)

2. Study Population

Adults at risk of HIV acquisition (determined by screening tools, self-report, and provider assessment) and eligible for pharmacy-delivered PrEP/PEP services (i.e., no medical conditions that might contraindicate PrEP/PEP safety) identified by screening at one of 60 participating pharmacies in Kenya whose data (pharmacy/clinic records, survey, and/or interview) were collected.

Pharmacies

Eligibility criteria:

- Registered with the Kenya Pharmacy and Poisons Board (PPB)
- Premises must comply with the requirements of the Pharmaceutical Society of Kenya and the Kenya Pharmaceutical Association
- Must have ≥1 full-time licensed pharmacist or pharmaceutical technologist on staff
- Must have a private room where HIV testing and PrEP/PEP counseling can occur

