- PrEP-to-PEP transition: the number of participants at each pharmacy that initiated (i.e. were dispensed) PrEP and subsequently initiated PEP at the pharmacy or clinic within 3 days, as measured at **60 days** and **270 days** following initial pharmacy screening.
- PEP/PrEP initiation: the number of participants at each pharmacy that initiated (i.e., were dispensed) either PEP or PrEP at the pharmacy or clinic (within 3 days for PEP clients) as measured at **60 days** and **270 days** following initial pharmacy screening.
- PEP/PrEP continuation: the number of participants at each pharmacy that (1) initiated PrEP and refilled PrEP or later were dispensed PEP; or (2) initiated PEP and transitioned to PrEP or later were dispensed PEP again as measured at **60 days** and **270 days** of initial pharmacy screening.

- Recurrent PEP use: the number of participants at each pharmacy that were dispensed PEP ≥ 2 times as measured at **60 days** and **270 days** of initial pharmacy screening.

Tertiary outcomes include related behaviors as well as implementation outcomes based on a variety of scales:

- Follow-up HIV testing: the number of participants at each pharmacy engaging in HIV testing following the pharmacy PrEP/PEP visit (not including the initiation visit), as measured at **60 days** and **270 days** following initial pharmacy screening.
- HIV risk: the number of participants engaging in specific self-reported behaviors associated with HIV risk reported in the time frame following pharmacy PrEP or PEP delivery, such as any condomless sex in the past month and self-reported perception of HIV risk acquisition in the present and future.
- PrEP coverage (exploratory): duration of time on PrEP based on dates of dispensing and the quantity of pills dispensed at each visit using all longitudinal data available at completion of the cRCT.
- Client implementation outcomes
 - Acceptability: assessed in the extended client survey at different time points over the trial duration using questions that measure different domains of the Theoretical Framework of Acceptability (Sekhon et al., 2017, *BMC Health Serv Res*), which consists of seven component constructs (e.g., affective attitude, burden, perceived effectiveness).

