 - Fidelity: the number and proportion of participants that received different core components of the intervention (e.g., counseling on HIV risk, medical history, HIV testing, drug dispensing) as specified in the protocol. Assessed in the extensive client survey at different time points over the trial duration.
 - Willingness to pay: the amount eligible pharmacy PrEP clients are willing to pay for each pharmacy PrEP or PEP visit, as assessed in the extensive client survey at different points in time over the trial duration.
 - Quality of care perceptions: assessed in the extensive client survey at different time points over the trial duration using a modified perceived service quality scale (pSQ-SF6) (Carter et al., 2022, *Res Social Adm Pharm*), with higher score indicating higher perceived service quality.
- Provider/counselor implementation outcomes
 - Acceptability: assessed in the provider survey at different time points over the trial duration using questions that measure different domains of the Theoretical Framework of Acceptability (Sekhon et al., 2017, *BMC Health Serv Res*), which consists of seven component constructs (e.g., affective attitude, burden, perceived effectiveness).

- Feasibility: assessed in the provider survey at different time points over the trial duration using questions based on the Feasibility of Intervention Measure (FIM) (Weiner et al., 2017, *Implement Sci*).
- Perceived self-efficacy: assessed in the provider survey at different time points over the trial duration using statements that assess providers' level of confidence delivering different core components of the pharmacy PrEP intervention (e.g., counseling, HIV testing, referral, etc.).
- Willingness to charge: the amount pharmacy providers are willing to charge for each pharmacy PrEP or PEP visit under different scenarios. Assessed in the provider survey at different time points over trial implementation.
- Pharmacy implementation outcomes
 - Sustainability: comparison of study outcomes during the first half and second half of implementation.
 - Adaptations: measured in the technical assistance reports using the Framework for Reporting Adaptations and Modifications to Evidence-based Implementation Strategies (FRAME-IS) (Miller et al., 2021, *Implement Sci*).

[figure not shown]
4 Study Design

The study is a cluster-randomized control trial (cRCT). The intervention will be introduced in a parallel fashion with a brief ramp-up period (i.e., staggered launch).

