	PEP initiation	By 60 and 270 days	
	PEP-to-PrEP transition	By 60 and 270 days	
	PrEP-to-PEP transition	By 60 and 270 days	
	Repeat PEP use	By 60 and 270 days	
	PrEP/PEP initiation	By 60 and 270 days	
	PrEP/PEP continuation	By 60 and 270 days	
	PrEP adherence	At 60 days	
			Brief client survey (self-report)
Tertiary	HIV risk behaviors	At 60 and 270 days	Brief client survey Extended client survey
	Follow-up HIV testing	At 60 and 270 days	
	PrEP coverage	Over study duration	Brief client survey Pharmacy records* Clinic records*
	Client: acceptability	At 60 and 270 days	
	Client: quality of care perceptions	At 60 and 270 days	
	Client: willingness to pay	At 60 and 270 days	Extended client survey Client interviews
	Client: fidelity		
	Provider: acceptability	At baseline, 60, and 270 days	
	Provider: feasibility	At baseline, 60, and 270 days	Provider interviews Provider surveys
	Provider: willingness to charge	At baseline, 60, and 270 days	
	Provider: perceived self-efficacy	At baseline, 60, and 270 days	
	Pharmacy: adaptations	Over study duration	TA reports
	Pharmacy: sustainability		Brief client survey Pharmacy records* Clinic records*

*The pharmacy records and client records will be used for comparison of outcomes between intervention arms and other secondary analyses; see Section 7.5 for details.

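### PrEP coverage is a raw duration with no common observation window, so each arm's average depends on enrolment date as well as on time on PrEP

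*SAP*

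**What the plan says.** SAP Section 3, under tertiary outcomes, defines PrEP coverage as time on PrEP, worked out from when PrEP was dispensed and the "quantity of pills dispensed at each visit using all longitudinal data available at completion of the cRCT". The Table 5 row in Section 6.2 reads "PrEP coverage Over study duration", whereas almost every other dispensing outcome there is tied to 60 days, 270 days or both. Section 7.5.2 states the whole analysis: "For the exploratory outcome of PrEP coverage, descriptive statistics in each arm will be provided".

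The overview table in Section 1 gives the calendar as "At least 20 months for accrual (until sample size achieved) plus follow-up of up to 270 days". Section 4 adds: "The intervention will be introduced in a parallel fashion with a brief ramp-up period (i.e., staggered launch". Section 4.4.3 lets back-up pharmacies replace those that drop out during implementation.

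On sources, Section 6.2 lists "Pharmacy records: intervention arms only, Arms 1-3 (i.e., not SOC arm, Arm 4" and "Clinic records: SOC arm only". The brief client survey covers all arms. Its listed items ask whether and where PrEP was started or refilled, whether it is still taken, and how many pills were swallowed in the last 7 days. They include neither dispensing dates nor quantities dispensed. Table 5 names all three sources for coverage but does not say how they are combined.

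**The concern.** A duration counted up to the end of the trial is bounded by how long each client was observed. Two clients who use PrEP identically get different coverage if one enrolled in month 1 and the other in month 20. Averaging such durations by arm mixes persistence with calendar time of enrolment, and the arm table gives the reader no way to separate them.

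The SAP handles unequal observation elsewhere. The primary model scales its offset for pharmacies that drop out (Section 7.5.1.1), and comparisons from pharmacy records stop at exactly 60 days (Section 7.5.1.3). Coverage depends directly on follow-up length and has no such rule.

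The arms would also sit side by side although the dated records behind Arm 4 come from a different system from those behind Arms 1-3.

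Coverage is the only listed outcome that measures length of use. A reader is likely to turn to it to see what happened after the 60-day outcomes.

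**Working it through.** The SAP gives no numerical target for coverage, so there is no figure of its own to reproduce. The check has two steps: the observation windows that its durations imply, and the effect of those windows on the mean when true persistence is identical.

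**Step 1: windows.** Inputs are 20 months of accrual and 270 days of follow-up (Section 1). Assumption: data end 270 days after the last enrolment.

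- Accrual: 20 × 30.4375 = 609 days.
- First client: 609 + 270 = 879 days, or 28.9 months.
- Last client: 270 days, or about 9 months.
- Ratio: 879 / 270 = 3.25. Accrual beyond 20 months would widen it.

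**Step 2: persistence.** The SAP gives no monthly persistence. Table 3 in Section 4.5 expects 50%, 70%, 80% and 60% of initiators in Arms 1 to 4 to continue. Assumption: read these as two-month retention at a constant monthly rate, so s = √p.

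Mean covered months with T months observed: C(T) = (1 − s^T)/(1 − s). With accrual spread evenly, average C over T = 19 to 29 for clients enrolled in the first half (E) and over T = 9 to 19 for the second half (L). C(9) represents records that stop at day 270.

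The average over an interval a to b is [1/(1 − s)] × [1 − (s^a − s^b)/((b − a)(−ln s))]. For p = 80%, s = 0.8944:

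- E = 9.472 × [1 − (0.1200 − 0.0393)/1.1157] = 8.79 months.
- L = 9.472 × [1 − (0.3664 − 0.1200)/1.1157] = 7.38 months.
- C(9) = 9.472 × (1 − 0.3664) = 6.00 months.
- All-early versus all-late: 8.787/7.381 = 1.19.
- 60/40 versus 40/60 early/late mix: (0.6 × 8.787 + 0.4 × 7.381)/(0.4 × 8.787 + 0.6 × 7.381) = 1.035.
- Full records under even accrual versus a day-270 stop: [(8.787 + 7.381)/2]/6.002 = 1.35.

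The same steps for all four planning values:

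| Table 3 continuation | s | E | L | C(9) | E vs L | 60/40 shift | Full vs day-270 stop |
|---|---|---|---|---|---|---|---|
| 50% (Arm 1) | 0.71 | 3.41 | 3.37 | 3.26 | 1% | 0.2% | 4% |
| 60% (Arm 4) | 0.77 | 4.42 | 4.28 | 3.99 | 3% | 0.7% | 9% |
| 70% (Arm 2) | 0.84 | 6.03 | 5.55 | 4.89 | 9% | 1.7% | 18% |
| 80% (Arm 3) | 0.89 | 8.79 | 7.38 | 6.00 | 19% | 3.5% | 35% |

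Each row compares two hypothetical arms with the same persistence, so every percentage is artefact.

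**Cross-check with another model.** With exponential time on PrEP of mean 60, 120, 180, 365 or 730 days (assumed values), the early-half to late-half ratio is 1.00, 1.04, 1.10, 1.27 and 1.44. Full records against a day-270 stop give 1.01, 1.09, 1.21, 1.47 and 1.72. The artefact is negligible when use is short and grows with long use.

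**After a common 270-day window.** Every client has the same maximum, so the ratio is 1.00 at any persistence.

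**The case against.** The strongest reply is that little depends on this outcome. It is labelled exploratory and is only described by arm, with no test or model. Section 3 also has fixed-window 270-day outcomes for any refill, at least two refills, and stopping and restarting. That stands, and it keeps the point minor. Those outcomes count events, however; none measures how long clients were covered.

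Second, enrolment date distorts the comparison of arms only if accrual timing differs by arm. The ramp-up is described as brief, training is by county, and arms are allocated at 3 or 4 pharmacies each within county groups, so a county-by-county launch should fall about equally on all arms. This also stands. It does not close the question, because replacement pharmacies start late and Section 7.5.1.1 reports that enrolment numbers depended heavily on arm.

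Third, the overview's follow-up of up to 270 days might be taken as a limit on coverage too. The definition and Table 5 do not apply it. If it was intended, the definition should say so.

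A reader might infer that coverage reflects enrolment date as much as time on PrEP, with same-behaviour arms differing by up to 90%. The documents do not support this. The figure is 14.1/7.4 months. It needs monthly persistence of 0.95 (two-month retention of 0.95² = 90%, above every value in Table 3), one arm enrolling only in the first half, and another observed only to day 270. Nor does the SAP say that any arm's records run longer: day 270 is a survey date, not a stated end of the clinic records. It shows only that the sources differ.

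**Conclusion.** The point holds as a minor one. As defined, coverage has observation windows from about 270 to about 879 days and no adjustment for them, so its mean depends on enrolment date as well as on use. Whether the comparison of arms is distorted is unknown, because it requires accrual timing or record length to differ by arm.

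Under the Table 3 percentages the artefact is about 1% to 19% for all-early against all-late enrolment, an extreme contrast. It is under 4% for a 60/40 shift, and about 4% to 35% if one arm's records are assumed to stop at day 270. These sizes rest on reading continuation as constant two-month retention; if those who stay on become steadily more persistent, the artefact would be larger.

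On sources, the supportable statement is that dated dispensing data are arm-specific and that the common survey, as listed, cannot supply the defined measure.

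**What to change.** - Define the main coverage summary as days covered, or the proportion of days covered, in the first 270 days after screening for every client. This matches the horizon of the other outcomes.
- State the source for each arm. Show Arm 4 (clinic records) separately from Arms 1-3 (pharmacy records), with a note that the two record systems differ.
- Keep the longer records as a time-to-stop curve censored at the end of data, and state the gap that counts as stopping.
- Date the change and label it post-unblinding, since Section 7.7 records unblinding on 6 November 2025.

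The cost is SAP wording, a truncation in the program and one added curve. The small downside is that dispensings after day 270 leave the main summary, though they remain in the curve. The post-unblinding label is unavoidable, but matters little for a descriptive exploratory outcome.
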